**SCHEMA**

**Study Design**

This is a single arm, pilot study to estimate the toxicity, effectiveness and safety of intensity modulated radiation therapy in patients treated with p16+/HPV+ oropharyngeal squamous cell carcinoma with reduced radiation dose to the lymph nodes at risk for microscopic disease but clinically staged as N0.

**Intensity Modulated Radiation Therapy**

- Patients will be treated with intensity-modulated radiation therapy (IMRT). Planning Target Volume (PTV1) will include the gross disease with expansions for microscopic disease extension and 3 mm setup error expansion and will receive 70 Gy/35 fractions at 2.0 Gy/fraction/day for 5 days/week of a 7 week regimen.
- PTV2 will include the clinically uninvolved cervical lymph nodes (N0 lymph node volumes) with a 3 mm expansion for setup error and will be treated to 39.6 Gy/22 fractions at 1.8 Gy/fraction/day for 5 days/week.

**ELIGIBILITY (see section 3)**

- Confirmed histopathologic diagnosis of p16-positive tumor by immunohistochemistry.
- Must undergo pre-treatment tumor staging using the version 7 American Joint Cancer Committee Staging System.
- Patients must undergo a PET CT within 8 weeks prior to cancer treatment.
- Patients must have a contrast neck CT within 8 weeks to cancer treatment (this can be the CT simulation) or if they have a CT contrast allergy this can be a neck MRI scan.
- Tumor must be measurable by physical exam and/or endoscopy, and PET CT.
- Primary diagnosis is clinical stage I-IVb (T1-T4, N0-N3, M0).
- 18 years of age or older.

- Able to lie flat on the table for IMRT and tolerate aquaplast or other immobilization systems that reduces intra-fraction motion to 3 mm or less.
- Able to understand English (or a medical interpreter for their native language must be available for all study visits).
- Zubrod performance status 0-2.
- Nutritional and general medical condition must be considered compatible with the proposed radiotherapy treatment.
- No prior radiotherapy to the head and neck in the volumes to be irradiated for this malignancy.
- No other malignancy except non-melanomatous skin cancer or a carcinoma not of head and neck origin with the patient being disease free for  $\geq 5$  years.
- No major medical psychiatric or neurologic illness, which in the investigators' opinions would interfere with either completion of therapy or with full and complete understanding of the risks and potential complications of the therapy.
- Mentally reliable to follow instructions and to keep appointments.
- Pregnant and breastfeeding women are excluded from this study.
  - Women of childbearing potential (WOCBP) must have a negative pregnancy test within 14 days prior to cancer treatment.
  - WOCBP and men agree to use adequate contraception (hormonal or barrier method of birth control) for the duration of radiation. Should a woman become pregnant or suspect she is pregnant while participating in this study, she should inform her treating physician immediately.
- Signed study-specific informed consent form.

**TREATMENT (see section **Error! Reference source not found.**):**

- Patients will be treated with IMRT. Planning Target Volume (PTV1) will receive 70 Gy/35 fractions at 2.0 Gy/fraction/day for 5 days/week.
- Clinically uninvolved cervical lymph nodes (N0 lymph nodes) will be treated to 39.6 Gy/22 fractions at 1.8 Gy/fraction/day for 5 days/week.

## **1 BACKGROUND AND RATIONALE**

### **1.1 Study Synopsis**

Oropharyngeal squamous cell carcinoma (OPSCC) is commonly treated with platinum-based chemoradiation followed by neck dissection(s) for locally advanced nodal disease. Radiation schedules conventionally include 70 Gray (Gy) in 35 fractions to macroscopic disease and 60 Gy to the clinically uninvolved cervical lymphatics at high risk for microscopic metastatic disease and 50-54 Gy to the clinically uninvolved cervical lymphatics at low risk for microscopic metastatic disease(1). Despite advances in technology and the utilization of intensity-modulated radiotherapy (IMRT), treatment still causes significant acute toxicity, long term morbidity, reduced functional status, and a poor quality of life for many patients. Since the expected toxicities for radiation for this group of patients is extremely high (See Expected Toxicities Table in section 8.1.2) there is a great need to develop less toxic radiation regimens with equivalent efficacy to current standard of care regimens. Specifically, strategies for personalized cancer care which reduce the toxicity of treatment for those patients with more sensitive disease are needed. Oropharyngeal carcinoma is increasing in incidence in the United States in non-traditional populations, i.e. non-ethanol and non-tobacco user groups, secondary to human papilloma virus (HPV) infection. HPV-associated tumors over-express p16, a protein easily detected by immunohistochemistry, and are more sensitive to chemotherapy and radiation than non-HPV-associated tumors. We recently reported a retrospective analysis of 112 oropharyngeal cancer patients treated with definitive IMRT +/- chemotherapy with 70 Gy to PTV1 and 50.4 Gy to PTV2 showing that p16-positive tumors are highly curable with 100% primary tumor local control, 90% sterilization of pathologic lymph nodes based on pathologic analysis of neck dissection data, and 100% control of the clinically uninvolved (N0) cervical nodes(2). Given that 100% of the N0 nodes are sterilized by 50 Gy with or without chemotherapy we propose reducing the radiation dose to the N0 cervical nodal volumes in patients with HPV-associated tumors, as determined by p16 immunohistochemical staining. We hypothesize that we can deliver 39.6 Gy to the N0 nodes in OPSCC patients with p16 positive tumors and reduce toxicity without compromising N0 nodal control, disease-free survival, or overall survival.

UVA treats approximately 20-25 oropharyngeal cancer patients annually with definitive radiation or chemoradiation. We anticipate an accrual rate of 15-20 cases per year over 3 years (n=45). We will recruit a total of 45 patients with Stage I-IVb, p16-positive OPSCC who are candidates for radiotherapy. All patients will receive IMRT as part of their cancer treatment and will be followed on this study for 3 years after treatment.

The purpose of this study is to test the overall hypothesis that reduced intensity radiation treatment (39.6 Gy) to the N0 nodes in OPSCC patients with p16 positive tumors can reduce toxicity without compromising treatment efficacy. This represents a 10% reduction from 44 Gy (the minimum dose that the current NCCN guidelines recommend for the elective treatment of N0 nodes of patients with squamous cell carcinoma of the head and neck) and a 20% reduction from our institutional standard of care of 50.4 Gy. Efficacy endpoints will include N0 nodal control, disease-free survival, and overall survival. Safety will be assessed by grading of acute and late radiation-induced toxicity including acute radiation dermatitis and late subcutaneous fibrosis, neck dissection complication rate, xerostomia and dysphagia.

## **1.2 Disease Background**

### **1.2.1 Epidemiology of Head and Neck Cancer**

Although head and neck cancer is relatively rare, accounting for roughly 5% of adult cancers(3), it is a devastating disease with significant treatment-associated toxicities. The American Cancer Society reports approximately 40,000-50,000 cases of head and neck cancer are diagnosed annually in the United States(4). Head and neck cancer represents a diverse set of tumors originating in the head and neck region that include squamous cell carcinomas of the upper aerodigestive tract above the thoracic inlet, salivary gland tumors, thyroid tumors, sarcomas, and rare sinus tumors(5). Squamous cell carcinomas make up the vast majority of head and neck cancers and can develop in the mucosa of various upper aerodigestive anatomic sites including the oral cavity, oropharynx, nasopharynx, nasal cavity, paranasal sinuses, larynx, and hypopharynx(5). The development of these tumors is often related to patient use of tobacco products and/or ethanol, but viruses (HPV and Epstein-Barr Virus) and immunosuppression are also etiologic factors(5). The most common head and neck cancer treated at UVA with radiation is squamous cell carcinoma of the oropharynx (OPSCC).

### **1.2.2 Standard Radiotherapy for OPSCC**

Head and neck cancer can metastasize to cervical lymph nodes and do so in a predictable pattern with initial involvement of the first nodal echelon and sequential involvement in lower cervical and contralateral nodal regions(6-8).

[figure not shown]
The Seventh Edition of the American Joint Committee on Cancer Staging Manual published in 2010 is the current staging system used by most physicians to stage head and neck cancer patients(9). Patients with stage I and II disease have a small primary tumor without clinical evidence of lymph node metastases and are managed with surgery or radiation therapy alone. Patients with stage III and IV

are generally considered to have locally advanced disease that is manifest by large primary tumors and/or clinically involved cervical lymph nodes. Therapy for these patients frequently involves multi-modality therapy based on the volume and location of both the primary tumor and lymph node disease and may include various combinations of surgery, radiation, cytotoxic chemotherapy (cisplatin, carboplatin, taxol, taxotere, 5-fluorouracil, capecitabine), and/or biologic therapy (Cetuximab, an anti-epidermal growth factor receptor antibody)(10).

Radiation therapy for oropharyngeal cancer can conceptually be thought of as treating two separate regions to be targeted by the radiation (target volumes). The first target volume is the planning target volume 1 (PTV1) which contains all known gross cancer including the primary tumor and all pathologic lymph nodes (See Figure 1). Planning target volume 2 (PTV2) contains all of the clinically uninvolved cervical lymphatics at risk for microscopic disease spread (termed the N0 neck). Standard treatment for oropharyngeal carcinoma is definitive radiation therapy with 70 Gy delivered to PTV1 and 44-64 Gy (commonly 50Gy) delivered to PTV2(11). Concurrent chemotherapy is delivered for patients with Stage III-IV disease, and patients with N2 and N3 cervical nodal disease may also undergo neck dissection(s) to resect the nodal disease at the completion of chemoradiation if this is still palpable or appears pathologic on post-treatment imaging.

Irradiation of these large volumes spanning the base of skull to the clavicles results in significant acute toxicity (fatigue, skin redness and blistering, sore mouth and throat, mucosal ulceration, loss of taste, dry mouth, thick secretions, cough, hoarseness, dehydration, and nausea) and late toxicity (dental decay, permanent dry mouth, swallowing difficulties, middle ear effusions, altered taste, osteonecrosis of the mandible, and hypothyroidism)(5). Given the significant toxicity associated with current treatment techniques for OPSCC, translational advancements that would reduce dose and toxicity are highly desirable.

Figure 1: Diagram of PTV1 and PTV2

Red = PTV1   Yellow= PTV2

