### **2.2 Secondary Objectives**

- 2.2.1** To evaluate safety and tolerability of treatment of p16+ OPSCCA treated with 39.6 Gy to the clinically uninvolved neck by overall incidence of adverse events, incidence of acute and late radiation-induced toxicities and subject-rated quality of life assessments.

**2.2.2** To estimate progression-free survival and locoregional recurrence-free survival in patients with OPSCCA following treatment with 39.6 Gy to the clinically uninvolved neck.

**2.2.3** To compare the dose volume histograms (DVH) of treatment plans for patients receiving 39.6 Gy to the N0 neck to the DVH of matched treatment plans with the standard 50 Gy to the N0 neck.

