## 5 EVALUATIONS AND ASSESSMENTS

### 5.1 Time and Events Table

**Table 1: Treatment Assessments**

Assessment	Pre-study 	Treatment (weeks 1-7)		Post IMRT
	once	daily	weekly	once 
Informed Consent	X			
Inclusion/exclusion	X			
History	X		X	X
Physical Exam 	X		X	X
p16 immunohistochemistry	X 			
PET CT scan	X 			
Contrast enhanced CT (or MR)	X 			X
Serum pregnancy	X 			
Vital Signs (BP, HR, temp)	X		X	X
Weight	X			
Zubrod Performance Status	X		X	X
Toxicity Assessments			X	X 
IMRT		X		
Disease status				X 
QOL questionnaires	X			

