### 7.3 Analyses

Point estimates and confidence interval will be calculated for all dichotomous endpoints (N0 control rate, locoregional control rate, AE specific rates). The Kaplan-Meier product-limit method will be used to estimate PFS and locoregional recurrence-freesurvival. Confidence intervals will be estimated for all efficacy endpoints. Under the assumption of exponential PFS we will estimate the exponential parameter ( $\lambda$ ) and test whether the data support the alternative hypothesis that  $\lambda=0.1335$  versus the null hypothesis that  $\lambda=0.0744$ . Repeated measure models will be used to describe the change over time in QOL as measured by questionnaire. Data from the treatment planning software which produces graphs on mean, max, minimum doses to structures, as well as volumes of particular structures receiving certain doses will be used to compare the dose volume histograms (DVH) of treatment plans for patients receiving 39.6 Gy to the N0 neck to the DVH of matched treatment plans with the standard 50 Gy to the

N0 neck (i.e., to quantify the difference in radiation dose to critical structures in the neck with the decreased dose regimen compared to standard practice).

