### 8.1.2 Expectedness

The expectedness of the adverse event will be determined by the Investigator based on current literature and the Investigator's experience. Below is a listing of the adverse events, and maximum grade of event, expected in this study:

Adverse Events with Possible Relationship to Study Treatment			Maximum Grade
Likely (>20%)	Less Likely (<=20%)	Rare but Serious (<3%)	
BLOOD AND LYMPHATIC SYSTEM DISORDERS			
Anemia			1
	Anemia		2
Lymphopenia			2
Lymph Node Pain			1
	Lymph Node Pain		2
CARDIAC DISORDERS			
	Tachycardia (any type)		2
EAR AND LABYRINTH DISORDERS			
Ear Pain			1
	Ear Pain		2
		Ear Pain	3
Hearing Impaired			1
	Hearing Impaired		2
		Hearing Impaired	3
Middle Ear Inflammation			2
Tinnitus			1
	Tinnitus		2
		Tinnitus	3
	Vertigo		1
		Vertigo	2
ENDOCRINE DISORDERS			
Hypothyroidism			1
	Hypothyroidism		2
EYE DISORDERS			
	Cataract		1
	Conjunctivitis		1
		Retinopathy	2
	Watering Eyes		1
GASTROINTESTINAL DISORDERS			
Dental Caries			2

	Dental Caries		3
Dry Mouth			2
	Dry Mouth		3
Dysphagia			3
		Dysphagia	4
Esophageal Stenosis			1
	Esophageal Stenosis		3
		Esophageal Stenosis	4
Gingival Pain			2
Lip Pain			1
	Lip Pain		2
Mucositis Oral			3
Nausea			2
	Nausea		3
Oral Pain			3
	Peridental Disease		3
Salivary Duct Inflammation			2
	Salivary Duct Inflammation		3
	Toothache		2
Vomiting			1
	Vomiting		3
GENERAL DISORDERS AND ADMINISTRATION SITE CONDITIONS			
Edema Face			1
	Edema Face		2
		Edema Face	3
Fatigue			3
Irritability			2
	Irritability		3
Neck Edema			1
	Neck Edema		2
		Neck Edema	3
Pain Generalized			2
INFECTIONS AND INFESTATIONS			
Mucosal Infection			2
	Mucosal Infection		3
	Otitis Media		2
	Sinusitis		2
	Soft Tissue Infection		2
	Tooth Infection		2
	Tracheitis		2
	Upper Respiratory Infection		2
		Upper Respiratory Infection	3
INJURY, POISING AND PROCEDURAL			
Dermatitis Radiation			2
	Dermatitis Radiation		3
	Injury to Carotid Artery		3
		Injury to Carotid Artery	4
INVESTIGATIONS			
Creatinine Increased			1 1
	Creatinine Increased		2 2
Lymphocyte Count Decreased			2
	Lymphocyte Count Decreased		3
	Platelet Count Decreased		1

		Platelet Count Decreased	2
Weight loss			1
	Weight Loss		2
		Weight Loss	3
White Blood Cell Decreased			1
	White Blood Cell Decreased		2
		White Blood Cell Decreased	3
METABOLISM AND NUTRITION DISORDERS			
Anorexia			3
		Anorexia	4
Dehydration			1
	Dehydration		2
		Dehydration	3
	Hyperkalemia		1
		Hyperkalemia	2

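### Five laboratory-detected toxicities are expected in more than 20% of patients but no blood test for them is scheduled, so their all-patient rates are lower bounds unless routine care tests everyone

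*Combined protocol and SAP*

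**What the plan says.** **Expected events.** The table in section 8.1.2 has six laboratory rows in the column for events expected in more than 20% of patients:

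- anemia, grade 1
- lymphopenia, grade 2
- "Hypothyroidism", grade 1
- "Creatinine Increased", grade 1
- "Lymphocyte Count Decreased", grade 2
- "White Blood Cell Decreased", grade 1

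The second and fifth rows describe the same finding, so there are five distinct abnormalities. Section 1.2.2 separately names hypothyroidism as a late effect: "late toxicity (dental decay, permanent dry mouth, swallowing difficulties, middle ear effusions, altered taste, osteonecrosis of the mandible, and hypothyroidism".

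**Schedule.** The only blood test in Table 1 is "Serum pregnancy", done once before treatment and, by its footnote, for women of childbearing potential. Table 2 has none. The prose in sections 5.2 to 5.4 agrees with the tables: history, examination, vital signs, imaging, questionnaires and toxicity assessment, but no blood count, chemistry or thyroid test at any time up to 36 months.

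**Analysis.** Objective 2.2.1 includes the "incidence of acute and late radiation-induced toxicities". Section 7.3 states: "Point estimates and confidence interval will be calculated for all dichotomous endpoints (N0 control rate, locoregional control rate, AE specific rates". Sections 4.3 and 7.4 make every treated patient evaluable for toxicity. Section 8.1.1 counts clinically significant laboratory changes as adverse events. No section says how to treat a patient who was never tested.

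**The concern.** At the listed grades these findings are largely silent. Symptoms may raise suspicion of hypothyroidism or anemia at a visit, but a laboratory value is still needed to establish them. With every patient evaluable and no rule for the untested, the natural calculation is cases found divided by patients treated, and a patient without a test then lowers the rate just as a patient with a normal test does.

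At stake is how the secondary safety result can be read. Section 1.4 says the study should show tolerability better than in historic controls, and incomplete testing moves these rates in the favorable direction. Unless the number tested is reported, a reader cannot distinguish a low incidence from a low level of testing.

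**Working it through.** **1. Count.** Six laboratory rows in the >20% column of section 8.1.2, five distinct findings. Of these, none has a scheduled test in Tables 1 and 2 or sections 5.2 to 5.4.

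**2. The plan's nearest figure.** The protocol states no precision for adverse event rates. For another proportion, locoregional control, section 7.2 gives a two-sided 90% interval of width 0.17 at n = 45 and a rate of 10%. An exact (Clopper-Pearson) interval has width 0.161 at 4/45 and 0.175 at 5/45, and 0.168 at the interpolated 4.5/45. This reproduces 0.17, so the same exact interval is used below.

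**3. Testing unrelated to outcome.** Let p be the true rate and t the share of patients tested. Then the expected rate over all patients is p × t. The protocol says only that p exceeds 20%. The range for p and all values of t are assumptions, because the documents give none.

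| True rate p | t = 100% | 80% | 60% | 40% | 20% |
|---|---|---|---|---|---|
| 20% | 20% | 16% | 12% | 8% | 4% |
| 30% | 30% | 24% | 18% | 12% | 6% |
| 40% | 40% | 32% | 24% | 16% | 8% |

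Take p = 30% and n = 45:

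- With full testing, 45 × 0.30 = 13.5 cases are expected. The chance of seeing 9 or fewer (20% or less) is 0.09.
- With 60% tested, 45 × 0.18 = 8.1 cases are expected, and that chance is 0.72. The exact 90% interval at 8/45 is 9.2% to 29.8%, which just excludes the true 30%.

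**4. Testing related to outcome.** Let a be the share tested among affected patients and u the share tested among unaffected patients.

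- Rate over all patients: p × a
- Rate over tested patients: p × a / [p × a + (1 − p) × u]

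With p = 30%, a = 80%, u = 30% (all assumed):

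- All patients: 0.30 × 0.80 = 24%
- Tested patients: 0.24 / (0.24 + 0.70 × 0.30) = 0.24 / 0.45 = 53%

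With p = 30%, a = 60%, u = 40%:

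- All patients: 0.30 × 0.60 = 18%
- Tested patients: 0.18 / (0.18 + 0.70 × 0.40) = 0.18 / 0.46 = 39%

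Since a cannot exceed 1, the expected all-patient rate never exceeds p if the test itself does not misclassify. The tested-only rate exceeds p whenever a is greater than u. Each denominator alone can mislead. The two together, with the number tested, show how much the result depends on testing.

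**The case against.** The table in section 8.1.2 classifies expectedness for reporting and is not a list of endpoints. The toxicity endpoints named in section 6.3 include no specific laboratory finding, and the six rows, at grade 1 or 2, fall outside its grade 3 or higher item. Section 8.1.1 limits laboratory events to clinically significant changes, and Table 4 does not require OnCore entry of grade 1 or 2 events judged unrelated or unlikely to be related. Routine care may test everyone, in which case nothing is understated.

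Much of this stands, and it lowers the weight of the point. It does not remove it. Section 6.3 also lists late radiation toxicity in general, objective 2.2.1 covers overall adverse event incidence, section 7.3 plans event-specific rates, and Table 4 does require entry of related grade 1 events within 30 days of radiation. Nothing in the protocol requires or records routine testing.

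A reader might infer more than the documents support:

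- *That understatement is certain.* It depends on routine practice, which the protocol does not describe.
- *That testing will be more frequent with chemotherapy and fade in later years.* Section 4.4.2 leaves chemotherapy to institutional guidelines and mentions no laboratory monitoring. No section describes testing by year.
- *That a low hypothyroidism rate will be reported as a benefit of 39.6 Gy.* The volumes in section 1.2.2 are PTV1 and PTV2 together, and only the PTV2 dose is reduced. The protocol gives no historical hypothyroidism rate, and section 7.3 plans no toxicity comparison with historic controls.
- *That the tested-only rate is the correct one.* The second calculation above shows that it can be further from the truth than the all-patient rate.

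**Conclusion.** The point holds in a limited form. Five distinct laboratory findings are expected in more than 20% of patients, none has a scheduled test, and the planned rates treat every patient as evaluable. Those rates will be too low unless routine care tests every patient at suitable times, and the planned report would not reveal which is the case.

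The size cannot be fixed from the documents. With testing unrelated to outcome, assumed shares tested of 20% to 80% turn a true 30% into an expected 6% to 24%. The effect is confined to secondary objective 2.2.1. The primary N0 endpoint, the sample size and the stopping rule are untouched. Severity is minor, and the remedy is a cheap improvement.

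**What to change.** No test needs to be added.

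1. Add case report form fields for thyroid, blood-count and chemistry results already obtained in routine care, with dates.
2. In section 7.3, for laboratory-defined adverse events, report the number of patients tested in each of two windows: start of treatment to 90 days after the last IMRT, and after day 90.
3. For each such event and window, give the rate over all treated patients, labeled as a lower bound, and over tested patients, with a note that it may be too high if symptoms prompted testing.
4. State in sections 7.3 and 7.4 that, when testing is incomplete, the all-patient rate is not to be read as incidence or as evidence of better tolerability.

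The cost is some extra data entry, smaller denominators and wider intervals for the tested-only rates. Selection in who is tested remains, but the reader can see its possible extent. Recording works best if it starts prospectively.
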